11.3 Analysis

The proportion of men who become ineligible by central pathology review will be estimated for each arm. The primary analysis will be done using data from eligible subjects, especially using Gleason scores from central review. However, all statistical analyses will be conducted for the data sets from eligible patients only, as well as all patients randomized in the sensitivity analysis.

Progression: PSADT will be calculated as \log_2 divided by the slope (the least squares estimator) of \log (PSA) observations over time using all available PSA measurements, starting from the time point at which we have three PSA measurements (i.e. the first

PSADT of a patient is calculated at month 6 using the PSA measurements collected at months 0, 3 and 6 if there are no missing PSA measurements.” In order to avoid any miscalculation, the PSADT will be calculated at the Alliance Statistics and Data Center, not by each individual site.

Time to progression data will be analyzed using the log-rank test for univariable analysis and the Cox’s proportional hazards regression for multivariable analysis adjusting for the stratification factors and other prognostic factors. For the patients who proceed to treatment with surgery, radiation, local ablative therapy or hormonal therapy before progression within the 2-year follow-up period, the progression time will be censored at the time of withdrawal for treatment.

A recent study in a similar cohort of men undergoing active surveillance (102) reported that PSA kinetics was not closely associated with progression on subsequent surveillance biopsies. In order to address this issue, as a secondary analysis, we will also compare time to progression defined only by Gleason sum on repeat biopsy ≥ 7 for men younger than 70 years and $\geq 4+3 = 7$ for men 70 years or older. Because of decreased number of events, the log-rank test using this definition of time to progression may not have enough power. For example, if the 2-year PGR for the control arm is only 10% by this new definition, then the log-rank test will have only 50% of power with 418 eligible patients with events or full 2 years of follow-up.

Time to Treatment: Probability to proceed to treatment within 2 years (binary observation) and time to treatment (censored time to an event observation) will be analyzed using the chi-squared test and the log-rank test, respectively. We expect that the control arm will have more patients receiving treatment and shorter time to treatment than the experimental arm because of anxiety.

QOL: Quality of life (anxiety and depression, prostate cancer symptom checklist) will be compared between the two arms. The time trajectory of QOL will be estimated using the generalized estimating equation method based on working independent correlation structure (103) and the slope of the time trajectory will be compared between the two arms (104). We will consider taking a log-transformation of QOL observations if it improves the linearity of the time trajectory of QOL. The significance of the two arm comparisons will be adjusted for multiple testing among different QOL subscales using the methodology of Bang, Jung and George (105).

Dietary Recall: Diets will be evaluated at baseline and at 12 and 24 months by a series of three separate 24-hour dietary recalls collected interactively via telephone interview. The increase (from baseline) in mean daily intakes of total vegetables, crucifers, tomato products, beans/legumes and fat will be compared between arms using a two-sample t-test at 12 and 24 months. We may consider transforming (e.g. using logarithm) the data to improve normality of the distributions and variance stabilization. Data will be catalogued and analyzed utilizing Minnesota Nutrition Data System (NDS) software (Nutrition Coordinating Center, University of Minnesota).

Plasma carotenoid analyses:

- (1) Plasma carotenoid concentrations (PCC) will be compared between the two arms using a two-sample t-test. A log-transformation of the PCC observations may be considered in order to improve the normality of the distributions and variance stabilization.
- (2) PCC will be correlated with PSADT for the patients. Descriptive analysis using scatter plots and regression analysis will be conducted. Intervention and known predictors including the stratification factors will be adjusted in multivariable analysis.
- (3) Time to pathological progression (i.e., Gleason sum on repeat biopsy ≥ 7 for men younger than 70 years and $\geq 4+3 = 7$ for men 70 years or older) will be regressed on PCC in AS patients using Cox’s regression method. Intervention and known predictors including the stratification factors will be adjusted in multivariable analysis.

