1.2 Active Surveillance (AS) for Lower-Risk Prostate Cancer

The concept that substantial proportions of men diagnosed with lower-risk prostate cancer are over-treated has fostered growing interest in a management approach known as active surveillance (AS). AS entails vigilant monitoring of men with localized, lower-risk prostate cancer by serial PSA measurements, frequent digital rectal examinations, and intermittent prostate biopsies. Intervention with surgery, radiation, or other therapies is reserved until patients show evidence of disease progression (9,11-16).

Active surveillance protocols for identification of patients with lower-risk disease vary by institution, but are generally similar. Clinical criteria for enrollment in a surveillance program typically include total PSA < 10 ng/mL, tumor that is non-palpable, or palpable but small on digital rectal examination (clinical stage T1 or T2) and lower-risk tumor characteristics on prostate biopsy, namely, low-grade (Gleason sum \leq 6) and low-volume (tumor evident only in a small number and percentage of biopsy cores) disease (9,11-16). Similarly, while there remains no clinical consensus, disease progression while on surveillance is broadly defined as a rapidly increasing PSA (manifested as decreased PSA doubling time or increased PSA velocity) or worrisome pathology on repeat biopsy (Gleason score \geq 7 or increased tumor volume) (9,11-16).

In carefully selected men with lower-risk prostate cancer, AS is a viable and safe treatment option. Warlick and colleagues, confirming earlier results (9), observed that patients followed on AS for up to 6 years who then progressed by PSA or pathological criteria and underwent surgery were just as likely to be cured of their disease as men who underwent surgery immediately after diagnosis (14).

Approximately 30% of patients on AS will progress based on current PSA or pathological criteria and thus receive intervention with surgery or radiation, typically within 2 years of beginning surveillance (11). The Hopkins data indicate that 31% of patients progress

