8.4 Clinic Visits

PSA Measures (Every 3 Months)

Serum PSA levels will be measured at baseline and at every 3 months thereafter. PSADT will be calculated as \log_2 divided by the slope (the least squares estimator) of \log (PSA) observations over time using the last three PSA measurements (44, 83, 100). An example of a PSADT calculator can be found at www.ASURE.ca.

History & Physical (Every 6 Months)

Participants will be evaluated in a urology clinic at initial assessment and every 6 months thereafter as per typical AS protocols and current standard of care (2-4, 11, 13). Patients must be weighed and their height measured according to the instructions in Section 8.1. Urological evaluations will be conducted by the GU Investigator or appropriate designee (e.g., medical oncologist, PA, NP) at each site. The baseline visit will include a DRE to confirm clinical stage. Since PSA and biopsy changes are much more sensitive for detecting clinical progression than changes in prostate examination among patients on AS (11), subsequent DRE will be performed at the discretion of the individual urologist. These results will not be used to define progression.

Prostate Biopsy (24 Months)

Prostate biopsy will be performed by the treating urologist at 24 months with a minimum of 10 tissue cores obtained utilizing a standard, extended biopsy pattern. This practice is consistent with current standard of care in the urological community. The urologist or the participant will have the right to secure a biopsy earlier than 24 months. Although DRE is commonly used in oncologic practice, it is not highly quantifiable for men with the very small, often non-palpable tumors of our study participants.

Blood Sample Submission (12, 24 Months)

Six-hour fasting blood samples will be collected at preregistration, 12 and 24 months and will be submitted to the Alliance Biorepository at Ohio State University (see Section 6.2.1) and analyzed for carotenoid and cholesterol concentrations.

Quality of Life Instruments (Every 6 Months)

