8.7.2 Clinical Criteria for Progression and Active Treatment

The primary outcome of interest in this prevention trial is disease progression defined by (a) PSA doubling time (PSADT) less than 3 years, (b) PSA above 10 at any time, or (c) Gleason score on repeat biopsy ≥ 7 for men younger than 70 years and $\geq 4+3 = 7$ for men 70 years or older. These criteria are drawn from one of the largest active surveillance studies to date, the Toronto cohort (12).

Participants who do not meet PSA or biopsy criteria for progression are strongly encouraged to remain on AS while in the study and not undergo treatment with surgery, radiation, local ablation, or androgen deprivation. These criteria reflect the current standard of care (11,12) and are as follows:

a) PSA doubling time (PSADT) < 3 years

b) PSA ≥ 10 ng/mL

If the treating physician suspects that a single measurement of PSA ≥ 10 ng/mL represents a spurious rise unrelated to cancer progression (e.g., clinical prostatitis, asymptomatic prostatitis in association with a viral syndrome, or instrumentation of the urinary/gastrointestinal tracts), a repeat PSA may be drawn up to 2 weeks later. If the repeat PSA value is less than 10 ng/mL, then that repeat PSA value shall be recorded for that visit. If the repeat PSA value ≥ 10 ng/mL, the first PSA value should be recorded for that visit.

c) Repeat biopsy

- $\geq 25\%$ of biopsy tissue cores positive for cancer
- $> 50\%$ of any one biopsy tissue core positive for cancer
- Men < 70 years at baseline: Gleason sum ≥ 7
- Men ≥ 70 years at baseline: Gleason sum $\geq 4+3 = 7$

It is recognized that some participants will elect to pursue treatment during the study despite not meeting these criteria for progression. These participants will be censored at the time they begin treatment.

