11.2 Design

Each patient will be followed for 24 months, and PSA will be evaluated every 3 months starting from baseline. Prostate biopsies are taken at baseline and 24 months.

The primary outcome of interest in this prevention trial is disease progression defined by (a) PSA doubling time (PSADT) < 3 years, (b) PSA ≥ 10 at any time, or (c) Gleason sum on repeat biopsy ≥ 7 for men younger than 70 years and $\geq 4+3 = 7$ for men 70 years or older. These criteria are drawn from one of the largest active surveillance studies to date, the Toronto cohort (12). Data from this cohort indicate that approximately 20% of patients on active surveillance will progress by these criteria: 14% by PSA doubling time and 8%-10% by Gleason score.

Thus, using the log-rank test with a two-sided $\alpha = 5\%$, a sample size of 418 will provide 80% power to detect a difference in progression rate (PGR) of 20% in the control and 10% in the experimental arm during 24 months of follow-up. Under the exponential distributions for the time to progression, the 2-year PGR of 20% vs. 10% corresponds to a hazard ratio (HR) of 2.118. Assuming 10% of dropout rate (including patients who are treated before progression), a total of 464 patients will be enrolled to this trial.

Centralized pathology review will be conducted on the tissue specimens of the first 50 patients. From an analysis of grading by community vs. Johns Hopkins pathologists, Gleason grading of adenocarcinoma in prostate needle biopsy tissue (106), Gleason score was changed from 3+4 by community review to 4+3 by Johns Hopkins review for about 14% of men and from 6 or below to 7 or above for about 8% of men. Assuming about 30% of men in this study will be >70 years old and these two types of changes occur uniformly over the whole range of age, we believe that no more than 10% of men will become ineligible for the study by the centralized pathology review. We will consider increasing the sample size by a maximum of 10% depending on the proportion of men who become ineligible by central pathology review.

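### As written, the PSADT event (log 2 / slope below 3 years) is also met by every negative slope, and no section says how a zero or negative slope is handled

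*Combined protocol and SAP*

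**What the plan says.** Section 11.3 (Progression) defines PSADT as log 2 "divided by the slope (the least squares estimator) of" log PSA over time, "using all available PSA measurements, starting from the time point at which we have three PSA measurements". The first value is therefore available at month 6, from months 0, 3 and 6. The calculation is done at the statistics and data center, not at the sites.

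Section 11.2 makes this component (a) of the primary endpoint: "a) PSA doubling time (PSADT) < 3 years". Section 8.7.2 has the same component in words: "a) PSA doubling time (PSADT) less than 3 years". Neither gives a lower bound.

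Section 8.4 repeats the formula but computes the slope "using the last three PSA measurements", where Section 11.3 uses every value.

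Two places bear on intent. Section 1.2 says that "disease progression while on surveillance is broadly defined as a rapidly increasing PSA (manifested as decreased PSA doubling time or increased PSA velocity". Section 11.2 plans for 14% progressing by PSADT, 8% to 10% by Gleason score, and about 20% overall. No section states a positivity condition or says what to do with a slope of zero or below.

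**The concern.** The quantity log 2 / slope is not monotone in the slope. As growth slows towards zero it rises without limit; at zero it is undefined; just below zero it jumps to a large negative number. Every negative number is below 3, so a one-sided inequality on PSADT takes in both fast-rising and falling PSA.

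PSADT is the largest planned component of the primary endpoint, it is assessed repeatedly from month 6, and the first event counts. If the rule were programmed exactly as typed, one negative slope at any visit would end a man's progression-free time. A diet that lowered PSA or kept it flat would then add events to its own arm. Section 11.4.1 allows the study to be considered for stopping when the log-rank statistic is below 0. The progression-rate check in Section 11.4.2 acts only when the control rate is under 20%, so an inflated rate would not trigger it.

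**Working it through.** **The plan's own figure.** HR = ln(0.8)/ln(0.9) = 2.118. With two-sided alpha 0.05 and 80% power, n per arm = (1.960 + 0.842)² × (1/0.20 + 1/0.10) / (ln 2.118)² = 209.07, or 418.1 in total; 418/0.9 = 464.4. The stated 418 and 464 reproduce. No PSADT formula enters this calculation, so clarifying the rule leaves it unchanged.

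**Sign of the rule (no assumptions).** With times 0, 0.25 and 0.5 years, the least-squares slope is [ln(third) − ln(first)]/0.5, and PSADT = 0.693/slope.

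| PSA at months 0, 3, 6 | Slope per year | PSADT (years) | Below 3 as typed? |
|---|---|---|---|
| 5.0, 5.4, 5.7 | 0.262 | 2.65 | yes |
| 5.0, 5.1, 5.2 | 0.078 | 8.84 | no |
| 6.0, 6.0, 5.9 | −0.034 | −20.6 | yes |
| 6.0, 5.7, 5.4 | −0.211 | −3.29 | yes |

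The slowly rising series is not an event, while the near-flat and falling ones are. On the slope scale the intended rule is one-sided: 0 < PSADT < 3 is the same as slope > ln(2)/3 = 0.231 per year.

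**How often the case arises at month 6.** The documents give no within-man variation, so take an SD of log PSA of 0.05, 0.10 or 0.15 as an assumption. The sum of squared time deviations is 0.25² + 0 + 0.25² = 0.125, so SE(slope) = SD/√0.125 = 2.83 × SD.

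- Truly flat PSA: P(slope < 0) = 50% for any SD with symmetric error.
- True doubling time of 10 years (slope 0.0693): P(slope < 0) = Φ(−0.0693/SE) = 31%, 40% and 44%.

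**What a literal program would do.** This simulation uses all available values at each 3-monthly visit, independent normal errors on log PSA, and assumed SDs of 0.05 to 0.20.

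| True PSA course | Rule | Flagged at month 6 | Flagged by month 24 |
|---|---|---|---|
| Flat | literal | 55%–84% | 89%–99% |
| Flat | slope > 0 required | 5%–34% | 5%–49% |
| 10-year doubling | literal | 44%–84% | 56%–99% |
| 10-year doubling | slope > 0 required | 13%–39% | 14%–59% |

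At SD 0.05, slowing PSA from a 10-year doubling time to flat would raise the 24-month literal event rate from 56% to 89%. With the positivity condition the rate falls from 14% to 5%.

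**The case against.** The strongest reply is that nobody would read the rule this way. A falling PSA does not double, so a doubling time below 3 years plainly means fast growth. Section 1.2 ties progression to a rapidly increasing PSA. The literal rule would flag more than half of men with flat PSA at their first assessment, which does not fit planning rates of 14% by PSADT and about 20% overall. The calculation is centralized precisely to avoid errors, and an anomaly of that size would be hard to miss.

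Most of this stands as evidence of intent. A reader might infer from the formula that men with falling PSA are being classed as progressed, or that an effective diet will be penalized in this trial. The documents do not support that: no section says such men are events, and nothing shows that the central program ignores the sign.

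The reply does not close the gap. Section 1.2 is background on how surveillance programs in general describe progression, and it notes that there is no consensus; it is not the endpoint definition. The background is also not consistent on direction: Section 1.3 lists decreased doubling times after a diet intervention among studies offered as support for slower progression. The planning rates come from an external cohort and show what was expected, not what the program computes. Central calculation protects only if the specification it follows is complete, and for slopes of zero or below it is not.

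**Conclusion.** The written rule for the PSADT component is wrong for negative slopes and silent on a zero slope. That follows from the formula alone. It is a defect in the specification, not proof of misclassification: the intended event is almost certainly a short positive doubling time, and harm depends on the inequality being coded literally.

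The unhandled case would be routine: half of month-6 slopes under a flat PSA, and 31% to 44% under a true 10-year doubling time. The latter range rests on an assumed SD of 0.05 to 0.15 and independent normal errors. The simulated flag rates rest on similar assumptions and describe only the literal coding. They should not be read as the expected bias of the trial.

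The difference between Sections 8.4 and 11.3 over which PSA values enter the slope is a separate, actual contradiction in the same definition, and it can change any man's PSADT.

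**What to change.** 1. In Sections 11.2 and 11.3, define the PSADT event for the analysis on the slope scale: least-squares slope of log PSA (natural log) greater than ln(2)/3 = 0.231 per year, equivalently 0 < PSADT < 3 years. State that a slope of zero or below is not a PSADT event.
2. Verify the central program with test series that include falling, flat and slowly rising PSA, such as those in the first table above.
3. Reconcile the wording of Section 8.7.2 and Section 8.4 with Section 11, including the last three values against all available values. Section 8.7.2 also bears on clinical management, so this point asks only that the passages agree and proposes no change to a clinical criterion.

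The cost is a sentence in each of Sections 11.2 and 11.3, a consistency edit elsewhere, and a short program check. The 3-year threshold and the 418 eligible / 464 enrolled stay as they are.

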4.0 ELIGIBILITY CRITERIA

4.1 Preregistration Eligibility

4.1.1 Histologic Documentation: The initial biopsy showing diagnosis of prostate cancer should be used for the purposes of determining eligibility. However, if a subsequent biopsy performed before patient enrollment shows that the patient is ineligible, he may not be enrolled to the study. Eligible patients must meet all of the following criteria:

- Biopsy-proven (consisting of ≥ 10 tissue cores) adenocarcinoma of the prostate diagnosed within 24 months prior to pre-registration.
- $< 25\%$ of biopsy tissue cores positive for cancer.
- $\leq 50\%$ of any one biopsy tissue core positive for cancer.
- Clinical stage $\leq T2a$.
- Patients who have prostate cancer with distant metastases are not eligible.

NOTE: If a patient undergoes a transurethral resection of the prostate (TURP) for benign prostatic hyperplasia (BPH), and prostate cancer is diagnosed incidentally from the TURP specimen, eligibility for CALGB 70807 cannot be determined from the TURP specimen. However, if the patient subsequently undergoes a minimum 10-core prostate biopsy within 2 years of prostate cancer diagnosis from the TURP, and

prostate cancer is detected in the biopsy specimen and meets the requirements above, the patient is eligible for this study. If prostate cancer is not detected in the biopsy specimen, the patient is not eligible.

- 4.1.2 Prior Treatment:** Patients who have had prior treatment for prostate cancer by surgery, irradiation, local ablative (i.e. cryosurgery or high-intensity focused ultrasound) or androgen deprivation therapy are not eligible.
- 4.1.3** Patients who have had a history of non-cutaneous malignancy (other than non-melanoma skin cancer) in the previous 5 years are not eligible.
- 4.1.4 Language:** Patients must be able to read and comprehend English language text and be able to understand spoken English over the phone.
- 4.1.5** Life expectancy of at least 3 years.
- 4.1.6** Patients who are currently taking vitamin supplements including lycopene and beta-carotene are eligible.
- 4.1.7** Patients receiving treatment with 5-alpha reductase inhibitors (e.g., finasteride, dutasteride) within 90 days prior to preregistration are not eligible. Treatment with these agents during the protocol intervention is not permitted.
- 4.1.8** Patients who are currently taking coumadin are not eligible.
- 4.1.9** Participants will be men aged 50 to 80 years.

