- 4.1.10** For men ≤ 70 years, biopsy Gleason score ≤ 6 ; for men > 70 years, biopsy Gleason score $\leq (3 + 4) = 7$.

4.1.11 Required Initial Laboratory Values:

- Serum PSA < 10 ng/mL

NOTE: Baseline PSA for determination of eligibility must be measured after discontinuation of any 5-alpha reductase inhibitors.

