8.7.3 Continuation of the Dietary Intervention

Patients should continue intervention and follow-up for the two-year duration of the study regardless of progression or electing to receive therapy.

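### The carotenoid and polymorphism analyses of PSA doubling time have no cut-off at active treatment, so post-treatment PSA falls can shrink the association to about zero.

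*Combined protocol and SAP*

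**What the plan says.** - **PSADT definition.** Section 11.3 divides log 2 by the least-squares slope of log PSA, "using all available PSA measurements, starting from the time point at which we have three PSA measurements". Section 8.4 instead computes it "using the last three PSA measurements".
- **PSA schedule.** "Serum PSA levels will be measured at baseline and at every 3 months thereafter" (Section 8.4). The Section 7.0 calendar runs to month 24. It waives the month-24 biopsy for men who have started definitive treatment, but contains no such waiver for PSA.
- **Follow-up after treatment.** "Patients should continue intervention and follow-up for the two-year duration of the study regardless of progression or electing to receive therapy" (Section 8.7.3). Section 6.2 requires the 12- and 24-month blood samples even after progression or therapy.
- **Primary endpoint.** Progression includes "PSA doubling time (PSADT) < 3 years" (Section 11.2). Sections 8.7.2 and 11.3 censor men who are treated before progression.
- **Correlative analyses.** "PCC will be correlated with PSADT for the patients" (Section 11.3, plasma carotenoid item 2). Section 11.5 correlates MnSOD, XRCC1 and GST with PSADT within each arm. Neither states a PSADT time point, a cut-off at treatment, or a rule for zero or negative slopes.
- **5-ARIs.** Section 4.1.7 excludes use within 90 days before preregistration and adds: "Treatment with these agents during the protocol intervention is not permitted". Section 4.1.11 adds: "Baseline PSA for determination of eligibility must be measured after discontinuation of any 5-alpha reductase inhibitors". Section 7.0 accepts a baseline PSA taken up to 3 months before preregistration.

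**The concern.** PSADT in these analyses is meant to describe how the cancer behaves under surveillance. The only definition in Section 11.3 takes in every PSA value, and values keep arriving after treatment. Treatment is selective: Section 1.2 describes men who progress as going on to intervention, and Section 1.4 puts the total reaching treatment at 42% (30% for progression, 12% for anxiety). The men whose PSA rises fastest are therefore likely to be the ones whose PSA is then pushed down, and they would enter the regression as if their disease were regressing.

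At stake are objective 10.1.2.2 (carotenoids and PSADT) and objective 10.3.2.1 (polymorphisms and PSADT). A real association could be reported as absent. Section 11.5 reads the strength of association arm by arm, so attenuation that depends on how many men are treated bears directly on that comparison.

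**Working it through.** **The plan's own figures.** HR = ln(0.8)/ln(0.9) = 2.118, as stated. Freedman's formula gives 62 events; 62/0.15 = 413.3, about 414, against the stated 418. This point neither disputes nor depends on that figure. The PSADT threshold of 3 years is a log-PSA slope of ln 2/3 = 0.231 per year.

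**One man.** Take nine PSA values at 0, 0.25, ..., 2 years (mean 1). Sxx = 2(0.25² + 0.5² + 0.75² + 1²) = 3.75. True PSADT is 2 years, so the slope is ln 2/2 = 0.347. He is treated after month 12, and PSA then stays at a fraction f of its month-12 value (f is assumed).

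- Rising part: 0.347 × (-0.625 + 2.5)/3.75 = 0.173. Here -0.625 is the sum of (t-1)t up to year 1, and 2.5 is the sum of (t-1) after it.
- Fall: ln f × 2.5/3.75 = 0.667 ln f.
- Fitted slope = 0.173 + 0.667 ln f. It is negative once f is below exp(-0.26) = 0.77.

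| f | slope per year | PSADT, years |
|---|---|---|
| 0.50 | -0.29 | -2.40 |
| 0.20 | -0.90 | -0.77 |
| 0.05 | -1.82 | -0.38 |
| 0.01 | -2.90 | -0.24 |

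The five values to month 12 give 2.00 years. The Section 8.4 rule does not help: his last three values (months 18, 21 and 24) all follow treatment, so his slope is 0 and PSADT is undefined.

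**The carotenoid correlation.** Simulation of 464 men, 150 runs per setting, under four sets of slope and noise assumptions (log-PSA noise SD 0.03 or 0.05) giving 13-20% PSA progression. Assumed: true carotenoid-slope correlation -0.20, PSA falling to 5% after treatment, and 12% of non-progressors treated. Ranges are across the four sets.

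| PSA progressors treated | r with slope, all values | runs with wrong sign | rank r, non-positive slopes coded as PSADT 100 years |
|---|---|---|---|
| 0% | -0.08 to -0.05 | 1-13% | 0.16 to 0.17 |
| 25% | -0.04 to -0.01 | 21-40% | 0.14 |
| 50% | -0.01 to +0.02 | 37-65% | 0.12 to 0.13 |
| 75% | +0.02 to +0.04 | 65-83% | 0.09 to 0.10 |

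With PSA cut off at treatment, r with slope is -0.17 to -0.20 and the rank correlation with the long-PSADT coding is 0.16 to 0.18. Under that coding the sign is wrong in at most 3% of runs.

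A second simulation (418 men, PSA at 0.1-1 ng/mL after treatment at months 9-22, 25-75% of fast risers and 0-12% of others treated) took -0.2 to between -0.02 and +0.05. The cut-off gave -0.17 to -0.18.

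**Scale.** On raw log 2/slope values the expected correlation is positive. Even with the cut-off, the rank correlation is -0.05 to -0.08, because negative doubling times sort below short positive ones. With all values it is -0.06 to -0.09. A cut-off alone does not repair this scale.

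**Primary endpoint.** In every setting the PSA event times were identical in 100% of men with and without post-treatment values.

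**5-ARI started on study** (noise-free, growth continuing, assumed PSA fall of 30% or 50%).

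- True PSADT 24 months, start at month 4: PSADT never falls between 0 and 36 months at any visit to month 24.
- True PSADT 12 months, start at month 4: still an event, at month 12 or month 21 respectively.
- Start at month 7 or 10, true PSADT 12-30 months: already an event at month 6.

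**Baseline PSA suppressed, flat afterwards.** With values at months 0, 3 and 6 the slope is -ln(1 - fall)/6 per month. A 50% suppression gives a PSADT of 6.0 months and 30% gives 11.7. If the baseline was drawn 4 months before randomization, these become 9.3 and 18.1. With 10% suppression PSADT is 40-61 months, which is no event.

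**The case against.** The quoted sentence defines progression, and for that use it is sound. A man treated before progression is censored, and a man treated afterwards already has his event. A reader might infer that post-treatment PSA hides fast risers in the primary analysis; the censoring rule in Sections 8.7.2 and 11.3 rules that out. This stands in full.

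The correlative objectives refer to AS patients, and Section 1.4 describes such men as not receiving active therapy. That suggests the authors did not intend post-treatment PSA to count. It defines no data window, however, and Sections 6.2 and 8.7.3 keep treated men in the dataset, so an analyst following the text would include those values.

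Reversal of sign is shown on the slope scale, whereas the plan names PSADT. This stands: with negative slopes coded as a long PSADT the result is attenuation, and on the raw scale post-treatment values change little because the scale itself fails.

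On 5-ARIs, a reader might infer that users escape progression, or that starts would be fewer in the diet arm because Section 9.4 links vegetable intake to fewer urinary symptoms. The documents support neither. Use is prohibited, so it is a deviation. A clear riser is hidden only by a start before the first PSADT at month 6, and not always then. The Gleason criterion remains available. Nothing links symptoms to 5-ARI starts by arm. The suppressed-baseline case is possible on the text but needs particular timing.

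**Conclusion.** The concern holds for the carotenoid-PSADT and polymorphism-PSADT analyses. As written they mix PSA kinetics under surveillance with treatment effect. An assumed true carotenoid-slope correlation of -0.20 becomes -0.08 to +0.04, against -0.17 to -0.20 with a cut-off. A change of sign is possible on the slope scale, not established. It depends on the share of progressors treated, the depth of the PSA fall and the coding of negative slopes, none of which the documents give. The polymorphism analysis shares the rule but was not simulated.

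The primary endpoint is not affected by surgery, radiation, ablation or hormonal therapy. What remains there is narrow: no section says how to handle PSA after a prohibited 5-ARI start. Sections 8.7.2 and 11.3 do not name these drugs as a reason for censoring, and do not say whether hormonal therapy covers them. Sections 4.1.7, 4.1.11 and 7.0 together allow a baseline PSA drawn soon after discontinuation. The documents give no count of such men and show no imbalance between arms.

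**What to change.** For item 2 of the plasma carotenoid analyses in Section 11.3 and for the PSADT analysis in Section 11.5:

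1. Use only PSA values taken before the first surgery, radiation, local ablation or hormonal therapy.
2. Name the time point, for example the slope over all such values to month 24, with at least three values required. Report how many men have too few.
3. Analyse the slope of log PSA (the 1/PSADT scale) instead of log 2/slope, so that zero and negative slopes are ordered correctly.
4. Reconcile the PSADT windows in Sections 8.4 and 11.3.

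This takes a few sentences and can be applied to PSA data already planned. The cost is fewer PSA points, and so less precise slopes, for treated men; some may have none.

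As a minor addition, run a sensitivity analysis of the primary endpoint that drops PSA values taken after any on-study 5-ARI start, and any baseline PSA drawn shortly after discontinuation, over an interval the sponsor fixes in advance. It needs 5-ARI start and stop dates; the documents do not show whether an existing form collects them. Sections 4.1.7, 4.1.11 and 7.0 should be reconciled on the timing of the baseline PSA.
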